Figure 1. fMRI of TM Cycling Run: An AFNI analysis of a 5-min TM-cycling task comprising alternating 45-sec epochs of TM practice and comparison task (eyes-closed mental counting by 2's). (A) The location and orientation of a brain slice. (B) The fMRI scan of this slice with the correlational analysis superimposed as colored pixels (correlation threshold = 0.45). A number of regions distributed across the brain slice display pixels indicating increased (blue) or decreased (orange) signal intensity. (C) Graph plotting the signal intensity over the 5-min cycling run for the pixel located in the basal forebrain noted by the arrow (TM, meditation epoch; CT, control task epoch). This picture is meant to convey the functionality of our acquisition and analysis system. Since the data is from only a single run one cannot draw any specific significant conclusion regarding neural change associated with the cycling. In addition, this subject has considerable artifact (grey areas signify signal dropout) often seen in ventral slices due to dental work and/or air-bone interfaces. (Color copies in Appendix; R21, *fMRI Study of Brain Mechanisms during Meditation*).

Constructed a map of the correlation of the task-reference function with the corrected fMRI images. The task-reference function is created by convolving a standard hemodynamic response function—a gamma variate function with parameters described by Cohen [170] on the time series of the boxcar design of 0's and 1's. The results are displayed based upon a chosen level of significance, as either response time series maps for scans across each epoch and the entire run, and anatomic image overlaid with pixels possessing significant (positive or negative denoted by color) correlation. Data from the few noncycling runs were analyzed but did not have sufficient SBQ periods to yield reliable comparisons. One subject had very few (and very short) SBQs and the other subject had very few SBQs. The noncycling runs were conducted last in the early protocol and after a considerable period of lying in the scanner. Subject selection in this application will maximize for the number of individuals with SBQs in both cycling and noncycling runs.

C.2.6. Results of Cycling Runs.

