The sequence of analysis includes: (1) discarding the initial three scans of each run due to magnetic instability; (2) correcting for movement artifacts by the co-registration of the time series using AIR (automatic image registration); (3) morphing the distorted fMRI image onto the accurate, high resolution MRI anatomic image, by registering fMRI images to the 8-shot EPI scan using AIR and registering the T1-slice to the 3D-volume using image intensity; (4) generation of statistical parameter maps from the *t*-statistics resulting from the multiple linear regression—a statistical parameter map (SPM) is a map of all pixel areas that exceed a specified statistical threshold and; (5) transforming the *t*-statistic maps into *Z*-statistic maps for statistical analysis. With large numbers—100 or more—the *t*-distribution approximates a *Z*-distribution [184]. These final statistical parameter maps will reflect significant fluctuations in signal intensity during the two conditions of the cycling tasks, after the contribution of other physiological variables have been statistically removed.

D.2.3. Statistical analysis.

One of the valuable characteristics of fMRI is that the relatively high signal to noise ratio allows detection of significant changes in signal intensity *within* a single subject [185]. The steps for statistical analysis of all data will include:

- (1) The SPM [184] for the runs in each condition will be examined. Areas of significant signal fluctuations will be determined using two criteria [92]: (a) the *Z*-statistic > 4.0, ($p < 10^{-7}$), and (b) the cluster must contain a minimum of four pixels that touch on the sides or corners (eight-neighborhood connectivity).
- (2) We will examine the first run for possible adaptation effects. If the first run differs significantly from subsequent runs, we will consider excluding the first run from the overall analysis.
- (3) The *Z*-statistic of significant areas of fluctuations in signal intensity are noted when they meet the criteria above and are in 2 of the 3 statistical parameter maps from multiple runs in the same condition.
- (4) These *Z*-statistics will be used in parametric analyses.

D.2.4. Sample size.

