D.6.5.1. Sequence of Analysis. First, we will create a dummy time-series of 1, or 2's that correspond to the scans before and during three conditions: IBH, SBQ or EC. The dummy time-series then will be convolved with the hemodynamic response model using the Cohen Model. This will yield the dummy independent variable that will be entered into the multiple linear regression analysis along with O₂ and CO₂ data. The scans for each of the periods will be dependent variables in the analysis. We will examine the resulting statistical parameter maps for clusters of pixels displaying significant fluctuations in signal intensity. The Z-statistic of the activated clusters that meet our criteria (D.2.3.) will be entered as variates in a repeated-measures ANOVA, with brain area as the factor and the period as the repeated measures.

D.6.5.2. Comparison between conditions: SBQ, IBH and EC. Condition differences will be assessed with two-way repeated measures ANOVA with brain areas and condition as factors, and the two periods (before and during the conditions) as the repeated measures. Individual comparison will be conducted if there are significant main effects.

- We expect no main effects for brain areas, indicating highly variable activation across brain areas yielding no consistent relations.
- We expect main effects for condition (SBQ, IBH, EC), indicating different brain mechanisms are active during each condition. For example, during IBH we expect higher levels of task effort and motor system activation, and possibly higher CO₂ levels to yield the predicted main effect.
- We expect main effects for the repeated measure (before and during). The 'before' periods may be somewhat similar, while the 'during' periods may be significantly different.
- We expect significant interactions, indicating differential involvement of some brain areas during the three conditions. For instance, the cerebral cortex may exhibit lower BOLD signal in both 'before' periods. However, the cortex is expected to be activated during IBH, while remaining low or reduced during SBQ.

D.6.6. Outcome. This experiment will help identify:

- (1) Neural mechanisms specific to the generation and maintenance of IBH, and the effects of hypercapnia and loss of mechanical respiratory activity on BOLD signal intensity.
- (2) Neural mechanisms specific to SBQ periods, as compared to a variety of brainstates, including, other meditation periods, IBH, and EC.

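### The per-pixel threshold Z > 4.0 is labelled p < 10^-7, but it corresponds to p < 3.2 × 10^-5 one-sided or 6.4 × 10^-5 two-sided

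*Protocol*

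**What the plan says.** Protocol D.2.2 converts the t maps from the multiple regression into Z maps, on the ground that "With large numbers—100 or more—the *t*-distribution approximates a *Z*-distribution [184".

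D.2.3 then sets the rule for a significant area: "a) the *Z*-statistic > 4.0, ($p < 10^{-7}$), and (b) the cluster must contain a minimum of four pixels". The second criterion in full is that "the cluster must contain a minimum of four pixels that touch on the sides or corners (eight-neighborhood connectivity").

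The scope is general: "The steps for statistical analysis of all data will include" this rule. A Z is noted only if the area meets both criteria and its fluctuations "are in 2 of the 3 statistical parameter maps from multiple runs in the same condition". The section ends: "These *Z*-statistics will be used in parametric analyses".

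Two later sections rely on the rule. D.5.4 refers back to D.2.2–D.2.3 and uses the resulting Z-statistics as the variate in the Aim 1 MANOVA. D.6.5.1 does the same for Aim 2: "The Z-statistic of the activated clusters that meet our criteria (D.2.3.) will be entered as variates in a repeated-measures ANOVA".

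D.2.3 does not say whether the threshold is one- or two-sided.

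**The concern.** A Z cut-off and its p-value are the same statement in two forms. Here they differ by more than two orders of magnitude, and nothing elsewhere in the protocol reconciles them.

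Two things are at stake. First, an analyst cannot tell which number governs. Programming 4.0 and programming the cut-off that gives 10^-7 produce different maps, and so may bring different brain areas into the Aim 1 and Aim 2 analyses. Second, a report that quotes p < 10^-7 for areas found at Z > 4.0 would overstate the per-pixel evidence.

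**Working it through.** **Inputs**
- Height threshold Z > 4.0 with stated p < 10^-7 (D.2.3).
- Reference distribution: normal, after conversion from t (D.2.2).
- Sidedness: not stated, so both are computed. Two-sided is plausible. The preliminary maps in Section C.2 showed "pixels possessing significant (positive or negative denoted by color) correlation", and D.5.4 expects increases in some areas and decreases in others.
- Image grid: 64 × 64 in-plane, 19 slices, field of view 24 cm, slice thickness 5 mm (D.2.1).

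**Step 1: try to reproduce the stated p**
- One-sided: 1 − Φ(4.0) = 3.167 × 10^-5. Ratio to 10^-7: 317.
- Two-sided: 2 × 3.167 × 10^-5 = 6.334 × 10^-5. Ratio: 633.
- Reading 4.0 as a t value moves further away. With 100 degrees of freedom the tail is 6.1 × 10^-5 one-sided and 1.2 × 10^-4 two-sided. With 600 it is 3.6 × 10^-5 and 7.1 × 10^-5.

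None of these gives 10^-7.

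**Step 2: find the Z that does give 10^-7**
- One-sided: Φ^-1(1 − 10^-7) = 5.199.
- Two-sided: Φ^-1(1 − 0.5 × 10^-7) = 5.327.
- Even Z = 5.0 gives only 2.9 × 10^-7 one-sided.

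**Step 3: size per map, before the cluster rule**

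The grid has 64 × 64 × 19 = 77,824 voxels. A voxel is 240/64 = 3.75 mm in-plane, so 3.75 × 3.75 × 5 = 70.3 mm³. The brain volume imaged is not given. Assuming 800 to 1,400 cm³, there are 11,378 to 19,911 brain voxels. Expected pure-noise pixels per map = voxels × p:

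| Voxels | Z > 4.0, one-sided | Z > 4.0, two-sided | p = 10^-7 |
|---|---|---|---|
| Whole grid, 77,824 | 2.5 | 4.9 | 0.008 |
| Brain, 11,378 to 19,911 (assumed) | 0.36 to 0.63 | 0.72 to 1.26 | 0.001 to 0.002 |

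**Step 4: could 10^-7 be the joint rate of both criteria?**

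Gaussian noise was simulated in-plane on 1,500 fields of 256 × 256 pixels. The share of pixels lying in a same-sign cluster of at least four touching pixels at |Z| > 4 depends on smoothness (full width at half maximum):

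| Smoothness, pixels | Share of pixels |
|---|---|
| 0 | none seen |
| 1.5 | 8 × 10^-8 |
| 2 | 1.1 × 10^-6 |
| 3 | 1.6 × 10^-5 |

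The 1.5-pixel figure rests on only 8 pixels (8.14 × 10^-8 × 98,304,000), so it gives an order of magnitude only. The protocol states no smoothness. D.2.2 lists no spatial filter, while D.6.4 adds a Hanning filter for the event-related images. No single joint p for all data follows from the plan.

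**Step 5: the rule of two maps in three**

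For the same pixel in three independent runs, 3p²(1 − p) + p³ = 3.0 × 10^-9 one-sided, and about 3p² = 1.2 × 10^-8 two-sided if the signs need not agree. This assumes independence and identical pixels, whereas the rule speaks of areas.

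**The case against.** The strongest reply is that Z > 4.0 is a usable rule and the bracket is only a label. Correcting the p-value alone would change no map, no cluster and no Z passed to the later analyses, and the hypothesis tests in this exploratory study come from those later analyses. That stands. It limits the harm to a misquoted p-value and doubt over which number governs.

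A reader might infer that every map and every Z carried forward is 300 to 600 times less stringent than claimed. The protocol does not support that. Maps also pass the four-pixel rule, and a Z carried forward also needs two of three maps. Steps 4 and 5 show that the combined rule can fall to the order of 10^-7 or below under some assumptions. The plan states no overall rate to compare against. These filters apply at either cut-off, however, and the bracket follows criterion (a), not the pair.

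A reader might also infer that p < 10^-7 promises whole-brain correction. D.2.3 makes no such claim; it gives a height cut-off and a cluster size.

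The bracket might be read as a further condition, with p < 10^-7 binding and Z > 4.0 redundant. D.2.3 counts only two criteria, which fits a gloss on Z better.

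Finally, the exponent appears once and may be a slip. At 10^-4 the line would be true on either sidedness (Z > 3.72 or |Z| > 3.89). That would explain the mismatch, not remove it. The cited source does not help: reference 92 is listed as a mortality follow-up of stress reduction in older hypertensive adults, not an imaging paper.

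**Conclusion.** The label is wrong as written. At Z > 4.0 the per-pixel p is 3.17 × 10^-5 one-sided or 6.33 × 10^-5 two-sided, so the stated figure is too small by about 317 or 633 times. This rests only on the normal reference distribution that the plan itself adopts. The choice between the two factors depends on the sidedness, which D.2.3 leaves open.

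The factor holds for the height criterion in one map. The false-positive rate of areas and Z-values entering the Aim 1 MANOVA and the Aim 2 ANOVA is lower by an amount the plan does not derive. The expected pixel counts in Step 3 are before the cluster rule, and the brain-only row rests on an assumed volume. The document does not show whether the Z or the p was intended.

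**What to change.** Change the one line in D.2.3, in one of two ways:

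- Keep Z > 4.0 and restate it as p < 3.2 × 10^-5 one-sided (or |Z| > 4.0, p < 6.4 × 10^-5 two-sided), uncorrected, per pixel.
- If p < 10^-7 is what was meant, raise the cut-off to Z > 5.20 one-sided or |Z| > 5.33 two-sided.

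State the sidedness in either case. D.5.4 and D.6.5.1 need no separate edit, since they refer back to D.2.3.

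The first option makes the stated p-value less favourable but leaves the maps as they would be at Z > 4.0. The second will detect fewer clusters. A simulated map-wise error rate for the combined height, cluster and replication rules would be informative but is optional; the correction does not depend on it.

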We will record fMRI (in first 10 subjects meeting inclusion criteria) during randomly ordered epochs of controls and TM practice. We will use two cycling ABC-run with eyes-closed. Each ABC-run comprises TM and two control conditions: (1) listening passively to nature (ie, ocean) sounds or (2) mental-counting by '2s'. An ABC-run (for example, using 30 sec epochs) will last about 22min, including 45 total epochs, 15 epochs each condition. This will result in 22 min/run x two epoch lengths = 45 min of testing, plus 40 min of preliminary anatomic scans, for a total time of less than 2 hr per MRI session. Whole-brain scans will be recorded from 19 slices per scan. At the end of each 22-min run, subjects will be asked to report their experiences. Carryover effects will be minimized by: (1) inserting one minutes breaks between runs. During these breaks we will be speaking and de-briefing the subjects; and (2) randomly presented control conditions in the same run. With this design, *within*-sets comparison will provide an estimate of the *minimal* carryover effects and *across*-sets will provide an estimate of *maximal* carryover effects.

D.5.4. Analysis for Hypotheses 1 & 2.

The data will be processed, and clusters of significant fluctuations in signal intensity will be noted (see Sect. D.2.2-D.2.3.). We expect clusters of fluctuations in signal intensity in 4-8 brain areas (see Sect. B.). The Z-statistics for areas of significant fluctuations in signal intensity will be noted from all runs and used as the variate in a repeated measures MANOVA. In this MANOVA, brain areas (4-8 estimate), and epoch condition (3) will be the factors, and the epoch-lengths (2) will be the repeated measure. For all main effects, individual comparisons will be conducted.

1. We expect **main effects for brain areas**, indicating significant differences in signal intensity between one or more brain areas. These changes may include in rank order: basal forebrain increases, slight cerebral and cerebellar cortex and mesencephalic reticular formation decreases, and no decreases in medial thalamus.
2. We expect **main effects for epoch condition**, indicating significant differences in signal intensity across the three different conditions—TM, passive-attending and mental-counting. These changes may include in rank order: de-excitation will be maximum for TM, then passive-attending, and lastly, mental-counting.

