The BOLD signal and physiological measures will be collected during four runs of 12 minutes duration each. Each 12 min run comprises three periods: 5 min uninterrupted meditation, 5 min structured breath-holding, and 2 mins non-task, eyes-closed (EC) control. The meditation period are free running with no interruptions from experimenters. During the meditation period we expect 3-5 SBQ periods. The breath-holding periods are structured by duplicating the previous SBQ pattern by voice command from experimenter, the onset and offset of IBH corresponding to SBQs time frame for each subject. The non-task control period will be determined from the outcome of experiment 1 (Aim 1), and either be passive-attending or mental-counting. The physiological measures will include respiration and transcutaneous CO₂ measurements. Four runs will take 48 minutes, or about 1 hr due to 30 rest periods between conditions. Therefore, each fMRI session will last about 90 minutes per subject.

D.6.4. Event-related fMRI analysis (Hypotheses 1-3).

Er-fMRI methodologies will be used to probe brain mechanisms during the onset of two conditions, during SBQ and IBH periods. The scans will be aligned relative to the onset of either SBQ or IBH during the four runs to permit signal averaging: 4 images before (12 secs) and 4 images after onset (12 secs). A TM meditator, selected in our screening protocol, may exhibit 25-30 spontaneous breath-quiet periods in a 30-min TM session [9, 20-22]. We estimate 12-20 periods will occur in our four meditation periods.

Images from individual runs will first be normalized to correct for the range of intra- and inter-subject signal intensity and temporal drift [171]. Specifically, normalization will involve: (1) scaling of signal intensity to a fixed value of 1000; (2) linear slope removal in a voxel-by-voxel basis; (3) spatial filtering with a one-voxel radius Hanning filter, and; (4) removal of the mean signal intensity on a voxel-by-voxel basis. The normalized fMRI images will then be aligned relative to the onset either SBQ or IBH periods. These images will be averaged within each subject. The mean image for each subject will be transformed into stereotaxic atlas space [208] using the highest point of the mid-sagittal plane and the anterior and posterior commissures. The atlas-transformed matrices will then be averaged across subjects.

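### Experiment 1 has one run per epoch length per session, so the 2-of-3-maps rule cannot be met as written for most or all subjects, and the first-run exclusion would remove one epoch length from a session

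*Protocol*

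**What the plan says.** D.2.3 is written for both experiments: "The steps for statistical analysis of all data will include" four steps.

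- Step 1 finds areas with Z above 4.0 and a cluster of at least four touching pixels.
- Step 2 looks for adaptation: "If the first run differs significantly from subsequent runs, we will consider excluding the first run from the overall analysis".
- Step 3 notes the Z-statistic of areas that meet the step 1 criteria and "are in 2 of the 3 statistical parameter maps from multiple runs in the same condition".
- Step 4 sends those Z-statistics to the parametric analyses.

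D.5.4 refers back to D.2.2-D.2.3 for Experiment 1. It enters the noted Z-statistics in a repeated-measures MANOVA, with epoch length (two levels) as the repeated measure.

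The Experiment 1 design is in D.5.3: "We will use two cycling ABC-run with eyes-closed". At 30-second epochs a run "will last about 22min, including 45 total epochs, 15 epochs each condition", so all three conditions sit inside each run. On session time it says: "This will result in 22 min/run x two epoch lengths = 45 min of testing, plus 40 min of preliminary anatomic scans", with a total under 2 hours. The randomisation described there concerns epochs within a run. Which epoch length is run first is not stated.

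The D.3 timeline allots 18 MRI sessions to Experiment 1, and D.5.3 names 10 subjects. In Experiment 2 (D.6.3) the data "will be collected during four runs of 12 minutes duration each".

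**The concern.** The replication rule presupposes three runs of the same kind. Experiment 1 supplies one run per epoch length in a session. If the rule is followed to the letter, Z-statistics from a subject with a single session never reach the MANOVA that tests Hypotheses 1 and 2. If it is relaxed without saying so, which areas enter that MANOVA becomes a choice made after seeing the maps.

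The first-run check has a related problem. With one run at each length, a difference between the first run and the later one could be adaptation to the scanner or an epoch-length effect, and that session cannot tell them apart. The remedy on offer, leaving out the first run, takes away the comparison that Hypothesis 1 needs. The result also feeds forward, because D.6.3 takes the Experiment 2 control condition from the outcome of Experiment 1.

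**Working it through.** **Reproducing the plan's session time.** Inputs from D.5.3: 45 epochs per run, 30 s per epoch (the protocol's example), two epoch lengths, 40 min of anatomic scans.

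- One run: 45 × 30 s = 1,350 s = 22.5 min.
- Two runs: 2 × 22.5 = 45 min, as stated.
- Session: 45 + 40 = 85 min, within the stated limit of 2 hours.

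The 45 minutes come out only with exactly one run per epoch length.

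**Maps available in a session against maps required.**

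| Reading | Maps per session | Rule needs |
|---|---|---|
| Per epoch length | 1 | 3 |
| Both lengths pooled | 2 | 3, and pooling merges the levels being compared |

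The three maps cannot be the three epoch conditions (TM, passive-attending, counting), because the rule asks for runs in the same condition.

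**Do repeat sessions rescue it?** Inputs: 18 sessions (D.3), 10 subjects (D.5.3).

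- Average: 18 / 10 = 1.8 sessions, hence 1.8 runs per length per subject.
- Three runs per length for all: 10 × 3 = 30 sessions, against 18.
- Three runs per length in one session: 6 × 22.5 + 40 = 175 min, against a limit of 120.
- Uneven allocation with every subject scanned at least once: 18 − 10 = 8 spare sessions, and a third session costs 2 of them, so at most 8 / 2 = 4 subjects reach three. At least 6 do not.
- Lenient reading, in which two agreeing maps are enough: 10 × 2 = 20 sessions, still more than 18.

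**First-run exclusion.** A session has two runs and two lengths. Removing run 1 leaves one run at one length, so that session has no within-subject epoch-length contrast. A subject with a second session would still have both lengths represented.

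**Experiment 2.** Four runs less the first leaves three, which fits the rule. If all four are kept, the text does not say how many of four are required.

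**The case against.** The best counter-argument is that D.2 is a generic standard protocol and D.5.4 has its own sentence, which takes Z-statistics for significant areas from all runs. On that reading the specific text governs and the 2-of-3 filter falls away. This has some force, and it disposes of one tempting inference, that no cluster could be declared in Experiment 1 at all: step 1 of D.2.3 declares areas from a single map. But D.5.4 opens by invoking D.2.3, and steps 3 and 4 of D.2.3 decide which Z-statistics go forward. The two texts still have to be reconciled.

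Other stronger readings a reader might draw are not supported:

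- *Epoch length is fully confounded with run order.* That would need the same order in every subject. The protocol is silent on order; it does not fix one. The one-minute breaks, debriefing and randomised epochs in D.5.3 do address carryover, but they do not say which length comes first.
- *Half the Experiment 1 data, or a whole epoch length, will be lost.* Exclusion is something the investigators will consider, and the loss depends on how sessions are allocated.
- *Within-subject variability across runs (D.5.5, D.5.6) cannot be estimated.* The 18 sessions allow some repeats, and D.4.2 mentions scanning the same subjects several times. The estimate is missing only for subjects with one session.
- *The rule fails in Experiment 2 as well.* It works there if the first run is dropped.

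The study is also exploratory, which bears on how strict a filter it needs. It does not make an uncomputable filter usable.

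**Conclusion.** The point holds for Experiment 1. A rule that the protocol states and applies to this experiment asks for three maps per condition, while the design gives one per epoch length per session. With 18 sessions and all 10 subjects scanned, at least 6 subjects cannot meet it, and none can if each has one session. This rests on the D.5.3 session layout and the D.3 session count, and on no assumption about effect size or power.

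The first-run problem is conditional: if the exclusion is invoked, that session loses one level of the Hypothesis 1 factor. Even if it is not invoked, first-run adaptation and epoch length are the same contrast within a session, and an unstated order leaves open whether they separate across subjects. Run order should be settled before scanning, since analysis afterwards cannot balance it.

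**What to change.** 1. In D.5.4, replace the 2-of-3 rule for Experiment 1 with a criterion the design can compute. One option is Z above 4.0 and the four-pixel cluster in the full run at each length, with consistency across thirds of the run shown descriptively.
2. In D.5.3, counterbalance which length is run first, 5 subjects each way, and include run order in the model.
3. State that the first-run exclusion in D.2.3 does not apply to Experiment 1.
4. For Experiment 2, state the number of maps required when all four runs are kept.

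No scan time is added. The costs are a weaker replication filter and one extra model term: for a simple paired contrast in 10 subjects, error degrees of freedom go from 10 − 1 = 9 to 10 − 2 = 8.

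Cutting each run into thirds and applying the 2-of-3 rule to them would also make it computable, but at a price. At TR 2.2 s (D.2.1) a 22.5-minute run has 1,350 / 2.2 ≈ 614 scans and a third has about 204. If Z grows with the square root of the number of scans (an assumption), Z = 4 in a third corresponds to about 4 × √3 ≈ 6.9 in the full run, so areas between 4 and 6.9 would tend to be lost. That is why the thirds are better kept descriptive.

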We determined sample size of 10 subjects based on published neuroimaging studies [111, 186]. The fMRI meditation study of Lazar et.al. [143] reported significant results with five subjects. Two PET studies of meditation [142, 144] reported significant signal changes with nine and four subjects, respectively. Litscher's recent study of Qigong [187] examined cerebral blood flow using two subjects, but reported no estimates of significance. Newberg et.al. [73] neural SPECT study of Tibetan meditation reported significant blood flow changes with eight subjects. An examination of 50 reports on PET or fMRI imaging of hypnosis, acupuncture, complex cognitive tasks, or simple sensory and motor stimulation showed that statistical significance was found with 10 or less subjects [see for example, 108, 111, 162, 188, 189-199].

D.5. Examine the Patterns of Neural Activity during the De-Excitation Substate (Aim 1).

Experiment 1: Selection of epoch length and control condition to image the de-excitation process.

D.5.1. Hypotheses. We will be testing two hypotheses in this experiment.**D.5.1.1 Epoch length.** We hypothesize that the shorter epoch length in a ABC-cycling protocol (randomly-ordered meditation and controls) will best 'frame' the initial de-excitation process due to significantly higher signal-to-noise ratio, higher signal intensity and less variance in the statistical test;

D.5.1.2. Control conditions. We hypothesize significant differences in signal intensity across the three different epoch conditions—TM, passive-attending and mental-counting, including in rank order: de-excitation will be maximum for TM, then passive-attending, and lastly, mental-counting.

D.5.2. Issues.

D.5.2.1. Epoch length. Epoch length will be pre-framed during our subject selection protocol. We will examine two epoch lengths centered on this preliminary value. The best frame will include maximum duration of the de-excitation process without the actual onset of a SBQ for most of the meditation epochs.

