3. We expect **main effects for the repeated measures**, indicating the epoch length that best framed the initial de-excitation of TM practice. For example, longer epoch lengths run the risk of introducing new, and variable cognitive and brain processes. This variability could result in lower signal-to-noise ratio, low signal intensity and more variance in the statistical test.
4. We expect **significant epoch length x epoch condition interactions**. We expect less cognitive and brain variability in the shorter epoch length regardless of condition resulting in greater distinction between epoch conditions. On the other hand, the greater variability of the longer epoch length may diminish the measured difference in signal intensity between conditions.

D.5.5. Outcome.

At the conclusion of this analysis, we should have empirical data sufficient to recommend the epoch length and the control condition to successfully image the initial de-excitation substate of TM practice. Secondary outcomes include consistency of signal intensity for regions of interest within subjects, and variability across runs between subjects. Anatomically, based on previous research-driven neural models (see Sect. B.2.5.), we would expect to at least find cortical de-excitation with possible exceptions of medial and ventral prefrontal cortices, accompanied with some basal forebrain, basal ganglia and brainstem excitation, cerebellar de-excitation and no change in medial thalamic activity.

D.5.6. Conclusion of Aim 1 Experiment.

From this experiment, we expect to find four basic outcomes regarding brain mechanisms during meditation from an ABC-cycling protocol:

- (1) The epoch length that appears to best frame the de-excitation process;
- (2) The effects of two different control conditions;
- (3) The brain areas that appear most closely correlated with the de-excitation process, as measured by the ABC-cycling protocol; and
- (4) The intra- and intersubject variability of activation/deactivation patterns;

Collectively, these findings will help formulate a working model of brain mechanisms during the de-excitation substate of TM practice.

D.6. Examine the Patterns of Neural Activity during the Maximum De-Excitation Substate (Aim 2).

Experiment 2: Comparing BOLD patterns across periods of differing mental & blood-gas conditions

D.6.1. Hypotheses. We will test five hypotheses in this experiment.

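### Epoch lengths are compared on Z-statistics that are read as signal intensity, so Aim 1 cannot tell a change in signal from a change in noise

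*Protocol*

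**What the plan says.** Hypothesis 1 (Section A and D.5.1.1) predicts that the shorter epoch frames de-excitation better because of "significantly higher signal-to-noise ratio, higher signal intensity and less variance in the statistical test". These are three separate claims.

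D.2.3 retains areas with Z above 4.0 in clusters of at least four pixels and sends their Z-statistics to the parametric analyses. D.5.4 follows this. The Z-statistics "will be noted from all runs and used as the variate in a repeated measures MANOVA"; brain area and epoch condition are factors, and "the epoch-lengths (2) will be the repeated measure". D.5.4 reads the area and condition effects as differences in signal intensity. It reads the epoch-length effect as "indicating the epoch length that best framed the initial de-excitation of TM practice", and D.5.5 draws the recommended epoch length from this analysis.

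On run length, D.5.3 says: "An ABC-run (for example, using 30 sec epochs) will last about 22min, including 45 total epochs, 15 epochs each condition". It then gives "22 min/run x two epoch lengths = 45 min of testing" and adds: "At the end of each 22-min run, subjects will be asked to report their experiences".

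**The concern.** The protocol names a test statistic as the outcome and interprets it as an amount of signal. A Z-statistic rises when the signal change is larger, when residual noise is smaller, when there are more scans, or when the design estimates the contrast more efficiently. A difference in Z between two epoch lengths does not show which of these occurred.

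This matters here because the protocol expects noise to change with epoch length. Item 3 of D.5.4 anticipates more variable brain processes in longer epochs, hence a lower signal-to-noise ratio, lower intensity and more variance. If only the noise changed, Z would fall and the plan would report a fall in intensity.

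Item 4 has the same weakness. Lower residual noise at the shorter length multiplies every condition's Z by the same factor and so widens the Z gaps between conditions. The expected interaction between epoch length and condition could then appear with no difference in signal change at all.

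At stake is one of the stated outcomes of Aim 1 (D.5.5, D.5.6), the choice of epoch length, and whether Hypothesis 1 can be tested in the terms in which it is written.

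**Working it through.** **1. The plan's own figures.** 45 epochs x 30 s / 60 = 22.5 min per run; 2 x 22.5 = 45 min; 45 / 3 = 15 epochs per condition. These agree with D.5.3.

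**2. What Z contains.** Let d be the signal change for a contrast, s the residual SD, and E = 1/sqrt(c'(X'X)^-1 c) the design efficiency, which grows with the number of scans. Then Z is approximately (d/s) x E. For a longer (L) and a shorter (S) epoch:

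Z_L / Z_S = (d_L/d_S) x (s_S/s_L) x (E_L/E_S)

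One observed ratio cannot identify three factors. For example, with equal E, a fall from Z = 5 to Z = 4 fits a signal change reduced to 4/5 = 0.80 with unchanged noise. It fits equally well an unchanged signal with residual SD raised to 5/4 = 1.25.

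**3. How large the E factor is.**

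Inputs from the protocol: TR 2.2 s (D.2.1); first three scans of each run discarded (D.2.2); epochs of 20 to 40 s (D.1). D.5.2.1 says only that two lengths will be centred on a screening value, so 20 versus 40 s is the widest case and 25 versus 35 s a narrower one.

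Assumptions not in the protocol: gamma-variate response parameters, conditions randomised in triplets, a linear trend, noise autocorrelation AR(1) of 0, 0.3 or 0.5, a TM-minus-counting contrast, and d/s held constant and scaled so that 45 epochs of 30 s give Z = 5.

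Scan counts:
- 22 min at both lengths: 1320 / 2.2 - 3 = 597 scans each (66 epochs of 20 s, or 33 of 40 s).
- 45 epochs at both lengths, 20 versus 40 s: 900 s gives 406 scans and 1800 s gives 815; sqrt(815/406) = 1.42.
- 45 epochs at both lengths, 25 versus 35 s: 1125 s gives 508 scans and 1575 s gives 712; sqrt(712/508) = 1.18.

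Expected Z with identical signal and noise, 20 s then 40 s:

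| AR(1) | 22 min per run | Ratio | 45 epochs per run | Ratio | 25 vs 35 s, 45 epochs: ratio |
|---|---|---|---|---|---|
| 0 | 4.83, 5.00 | 1.04 | 3.99, 5.85 | 1.47 | 1.20 |
| 0.3 | 4.89, 4.97 | 1.02 | 4.03, 5.81 | 1.44 | 1.19 |
| 0.5 | 5.01, 4.91 | 0.98 | 4.13, 5.74 | 1.39 | 1.17 |

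Adding slow-drift terms with a 256 s cut-off moves the 22-minute ratio to 4.81/4.95 = 0.97 (AR 0) and 4.81/5.01 = 0.96 (AR 0.3), which is still small.

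**4. Which run-length reading the text supports.** The 45-minute total does not decide it: 22.5 + 22.5, 15 + 30 and 18.75 + 26.25 all equal 45. The per-run statements do: a 15-minute or a 30-minute run is not a 22-minute run.

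**The case against.** The strongest defence is that Z suits a methodological choice. With equal run durations it measures how detectable the effect is, which bears on the signal-to-noise and variance parts of Hypothesis 1. An exploratory study may reasonably prefer the cycle length that detects best. This stands, and it is a reason to keep Z as a separate detection measure. It does not rescue the signal-intensity reading, which D.5.4 states outright and which one Z cannot support. Nor can it be left to a later analysis plan, because the protocol itself fixes both the variate and its interpretation.

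A reader might go further and infer that the longer epoch must score higher because its run has more scans, so that run duration decides the Aim 1 recommendation. The documents do not support this. The 45 epochs appear only in an example for 30 s epochs, while "22 min/run x two epoch lengths = 45 min of testing" and "At the end of each 22-min run, subjects will be asked to report their experiences" apply one run time to both lengths. On that reading the scan counts are equal and the artefact nearly vanishes, with no consistent direction. What remains is that 45 epochs and 22 minutes cannot both hold at lengths other than 30 s, and D.5.3 does not say in terms which one gives way.

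**Conclusion.** The point holds as a flaw in the choice and reading of the variate. D.5.4 cannot separate the intensity, signal-to-noise and variance claims of Hypothesis 1, and it would report a pure noise difference between epoch lengths as a difference in signal intensity. This follows from the definition of Z and needs no assumption about run length.

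The scan-count component is negligible on the indicated reading of equal 22-minute runs: a Z ratio of about 0.98 to 1.04 under the stated response and noise assumptions, and 0.96 to 0.97 with extra drift terms. An inflation of 17-20% (25 versus 35 s) to 39-47% (20 versus 40 s) in favour of the longer epoch, against the protocol's own hypothesis, arises only if 45 epochs were kept at both lengths.

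No false-positive rate is attached. It would depend on run-to-run variation within subjects and on correlation between areas, and the protocol gives neither.

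**What to change.** In D.5.4, make the regression coefficient, or percent signal change, the variate for the signal-intensity comparison. Take it for TM against each control, per area, subject and epoch length, from the same set of areas at both lengths, so that the Z threshold does not decide which length contributes. Compare residual noise between the two lengths separately, and report Z or a signal-to-noise measure beside it as a detection criterion. Each part of Hypothesis 1 then has its own comparison, and the recommendation in D.5.5 can say which part it rests on.

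In D.5.3, add one sentence stating that run duration (22 min) is held constant across epoch lengths and that the number of epochs is adjusted to fit; the count of 45 belongs to the 30 s example.

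The cost is a little more analysis on data already collected, and unequal epoch counts (66 versus 33 in the widest case). Planned scan time does not change.
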